### 5.1.3 Potassium Measurements

A further secondary objective of the study (see [Section 2.2](#)) is to determine whether the addition of oral sodium zirconium cyclosilicate (Lokelma®) during the 2-month treatment phase with the 3.0 K+/2.5 Ca++ dialysate bath will reduce the number of days outside the “K+ safety range” of 4.0 to 5.5 mEq/L compared to the 2-month treatment phase with the 2.0 K+/2.5 Ca++ dialysate bath.

K+ Piccolo POCT will be performed weekly during the two 8-week Treatment phases, as follows: pre-dialysis, and promptly before dialysis termination and 30 minutes prior to rinse back (along with Ca++ and PO4 measurements); see [Section 4.2.1](#).

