## **5.3 Safety Protocols**

### **5.3.1 Safety Protocol for Patients with Piccolo POCT-Confirmed Hypokalemia or Hyperkalemia**

Hyperkalaemia will be defined as a  $K^+ \geq 7.0$  mEq/L and measured using Piccolo POCT technology in pre-dialysis obtained after the long dialysis “weekend”. Unless clinically unstable, patients with hyperkalaemia will be dialyzed and managed according to the judgment of the Site PI. Dose adjustments of Lokelma will be with each patient prior to discharge.

Hypokalemia is defined as pre-dialysis  $K^+$  level of  $< 3.5$  mEq/L. Patients experiencing a minimum of two (2) hypokalemic events while taking Lokelma will have their Lokelma adjusted or discontinued at the discretion of the site PI.

Patients with clinically significant cardiac arrhythmias including bradycardia, ventricular tachycardia, and asystole that are recognized by the dialysis staff during an individual dialysis session will be managed according to site unit protocols and include necessary resuscitation and transfer to the nearest emergency department.

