## 6.9 Management of IP-related Toxicities / Dose Reductions

The study drug (Lokelma) will be titrated from 5.0 grams per day (4 days/week) up to a maximum of 15.0 grams per day (4 days/week), to maintain  $K^+$  within the desired target range (between 4.0 and 5.5 mEq/L). potassium levels will be regularly monitored, and the study drug dose adjusted based on the potassium levels (i.e., increased [up to a maximum of 15.0 grams/day] if potassium is  $>5.5$  mEq/L, or decreased if potassium is  $<4.0$  mEq/L).

As described in [Section 3.9](#), the study drug will be permanently discontinued in case the patient develops any of the following IP-related events:

- Two (2) or more hypokalemic events (defined as pre-dialysis  $K^+$  level of  $<3.5$  mEq/L);  $<$

Refer to [Section 3.9](#) for further details on events requiring permanent discontinuation of the study drug.

Safety protocols for the management of intra-dialytic events are provided in [Section 5.3](#).

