## 7.2 Dose and Treatment Regimens

### 7.2.1 Dosing Regimen

Patients will take Lokelma supplementation on off-dialysis days (4 days/week) while receiving hemodialysis with 3.0 K+/2.5 Ca++ mEq dialysate bath (8-week treatment phase):

- Patients on a Monday-Wednesday-Friday dialysis schedule will take the study drug on Tuesday, Thursday, Saturday, and Sunday
- Patients on a Tuesday-Thursday-Saturday dialysis schedule will take the study drug on Monday, Wednesday, Friday, and Sunday.

The individual starting dose will be 5.0 grams (4 days/week), and will be titrated weekly in 5.0 gram increments up to a maximum of 15.0 grams (4 days/week) to maintain K+ within the desired target range (between 4.0 and 5.5 mEq/L):

- Patients who fail to achieve a pre-dialysis K+ of  $\leq 5.5$  mEq/L after one week of 5.0 grams Lokelma will be treated with 10.0 grams on off-dialysis days for an additional 7 days.
- Patients failing to achieve a pre-dialysis K+ of  $\leq 5.5$  mEq/L after one week of 10.0 grams Lokelma will have their study drug dose increased to 15.0 grams.
- Patients failing to achieve the target K+ after a 7-day course of 15.0 grams Lokelma on off-dialysis days will be considered a treatment failure and withdrawn from the study.

Potassium levels will be regularly monitored throughout the 8-week treatment phase, and the study drug dose adjusted based on the potassium levels (i.e., increased [up to a maximum of 15.0 grams/day] if potassium is  $>5.5$  mEq/L, or decreased if potassium is  $<4.0$  mEq/L).

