**Table 3 IP Dispensing Schedule and Dosing Instructions**

IP Dose Level	IP Packets dispensed	Instructions for Patients (For dosing on off-dialysis days):
5.0 grams, 4 days/week	4 x 5.0 g packets	On each dosing day (4 off-dialysis days per week): Dissolve in water and drink the content of one 5.0 gram packet [1]
10.0 grams, 4 days/week	8 x 5.0 g packets	On each dosing day (4 off-dialysis days per week): Dissolve in water and drink the content of two 5.0 gram packet [1]
15.0 grams, 4 days/week	12 x 5.0 g packets	On each dosing day (4 off-dialysis days per week): Dissolve in water and drink the content of three 5.0 gram packet [1]

[1] Patients should be instructed to (i) empty the entire contents of the packet(s) into a drinking glass containing approximately 3 tablespoons of water or more if desired; (ii) stir well and drink immediately; (iii) if powder remains in the drinking glass, add water, stir, and drink immediately; (iv) repeat until no powder remains to ensure the entire dose is taken.

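### The Lokelma decrease rule in 7.2.1 and 6.9 cannot be applied consistently: it names no sample, has no defined step below the 5 g starting dose, and is not tied to the hypokalemia rule in 3.9 and 5.3.1

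*Protocol*

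**What the plan says.** Section 7.2.1 starts Lokelma at 5.0 g on four off-dialysis days a week and titrates weekly in 5.0 g steps to at most 15.0 g, aiming at 4.0 to 5.5 mEq/L. The up-titration steps are tied to a named sample; the first opens "Patients who fail to achieve a pre-dialysis K + of" no more than 5.5 mEq/L. The closing paragraph is general: "Potassium levels will be regularly monitored throughout the 8-week treatment phase, and the study drug dose adjusted based on the potassium levels", that is, increased above 5.5, "or decreased if potassium is $<4.0$ mEq/L". Section 6.9 has the same rule: "potassium levels will be regularly monitored, and the study drug dose adjusted based on the potassium levels". In neither place does the decrease clause name the sample, the number of readings or the size of the step.

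Potassium is measured weekly at two points of the same session, which section 5.1.3 gives as "pre-dialysis, and promptly before dialysis termination and 30 minutes prior to rinse back". Footnote 2 of Table 1 confirms the second reading.

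Table 3 dispenses three levels. The lowest is 5.0 g, supplied as "4 x 5.0 g packets" per week. Section 7.1 lists 5 g packets only.

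Sections 3.9 and 5.3.1 define a hypokalemic event as a pre-dialysis potassium below 3.5 mEq/L and say: "Patients experiencing a minimum of two (2) hypokalemic events while taking Lokelma will have their Lokelma adjusted or discontinued at the discretion" of the site investigator. Section 3.9.1 says Lokelma can be stopped abruptly and may be restarted at the investigator's discretion.

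**The concern.** Titrated Lokelma is half of the experimental regimen; the other half is the 3.0 K bath. Its dose rule should return one action for a given weekly potassium profile. As written it can return two opposing actions, or one that cannot be carried out.

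If a site applies the decrease clause to the end-of-dialysis value, it lowers Lokelma in a patient whose pre-dialysis value may be on or above target. That works against the interdialytic control the drug is there to provide. If another site applies it to the pre-dialysis value only, the same patient gets a different dose. Secondary endpoint 2, potassium outside 4.0 to 5.5, depends directly on this dosing. Low values are also a safety matter, so it should be clear what a site does after the first one.

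**Working it through.** No power, alpha or event figure is involved. The check applies the written rules to the possible readings. Let P be the pre-dialysis and E the end-of-dialysis potassium at one weekly session.

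**(a) Sample**

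- Increase (7.2.1 bullets; also 7.5): P > 5.5.
- Decrease (7.2.1, 6.9, read literally): any potassium < 4.0, so P < 4.0 or E < 4.0.
- If only P counts, P > 5.5 and P < 4.0 cannot both hold, and there is no clash.
- If E also counts, both rules are met whenever P > 5.5 and E < 4.0. This needs a fall during dialysis of more than 5.5 − 4.0 = 1.5 mEq/L.

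| Example session | Decrease rule uses P only | Decrease rule uses any value |
|---|---|---|
| P = 5.8, E = 3.7 (fall 2.1) | increase | increase and decrease |
| P = 5.0, E = 3.7 (fall 1.3) | no change | decrease |

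The second row shows that the two readings give different doses even where the increase rule is not met.

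The text does not settle which column applies. The bullets that name the pre-dialysis value govern increases and treatment failure. Where the protocol means a pre-dialysis value in the hypokalemia rules (3.9, 5.3.1, 6.9) it says so. It also applies the same 4.0 to 5.5 range to post-dialysis potassium as a secondary endpoint (2.2, 8.4.3), which gives a site a textual reason to apply 4.0 to E.

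**(b) Floor**

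One step down the ladder in Table 3:

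- 15 − 5 = 10 g, listed
- 10 − 5 = 5 g, listed
- 5 − 5 = 0 g, not listed

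A patient on 5 g with potassium below 4.0 is to be *decreased*, but no lower level exists. Section 3.9.1 allows stopping and restarting, yet nothing says that a decrease from 5 g means stopping. *Adjusted* in 3.9 and 5.3.1 has the same gap when the adjustment is downward from 5 g.

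**(c) Relation of the two thresholds**

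| Pre-dialysis finding | 7.2.1 and 6.9 (titration) | 3.9 and 5.3.1 |
|---|---|---|
| 3.5 to below 4.0 | decrease | silent |
| First value below 3.5, e.g. 3.3 | decrease | silent |
| Second value below 3.5 | decrease | adjust or discontinue, investigator's discretion |

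If every value below 4.0 already lowers the dose, the *adjusted* option after two values below 3.5 adds nothing. No section says how the rules fit together.

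A neighbouring conflict lies in the same text. For two or more such events section 6.9 says "the study drug will be permanently discontinued in case the patient develops any of the following IP-related events" and cites 3.9, which leaves the choice to the investigator, while 3.9.1 permits restart. It is a separate matter from the decrease rule, but the same passages must be reconciled.

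**The case against.** The best defence is context. The disputed clause follows bullets that name the pre-dialysis value. Section 7.5 ties up-titration to the pre-dialysis value after the long weekend, and hypokalemia for dosing purposes is defined as pre-dialysis. A sensible site would carry that over, and the opposing-instructions case would vanish. That is a reasonable reading, but it is an inference: those passages concern increases or a different threshold, and the end-of-dialysis value is judged against the same range elsewhere.

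On the floor, the defence is that 3.9.1 already provides for stopping and restarting. It does, but it does not link this to the decrease rule.

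On the thresholds, a reader might infer a flat contradiction, with 3.9 and 5.3.1 allowing a lower dose only after two values below 3.5. The documents do not support that. Neither section limits action in that way; one lists reasons for discontinuing the drug and the other is a safety protocol. Silence after a first value of 3.3 is not an instruction to do nothing, so both rules can be followed together as a titration tier and a safety tier. This part of the defence stands, and what remains is that the tiers are not stated.

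Finally, each patient is compared with himself or herself in the cross-over, so differences between sites in titration do not of themselves bias the treatment comparison. That also stands.

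**Conclusion.** The point holds as a defect in the dosing rule. Parts (a) and (b) rest on the text alone: the decrease clause names no sample although two are taken each week, and a decrease is undefined at 5 g, one of three levels and the one where every patient starts. Part (c) is a failure to relate two rules, not a contradiction between them.

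The size cannot be put in numbers. It would depend on how often end-of-dialysis potassium falls below 4.0 on the 3.0 K bath, and how often this coincides with a pre-dialysis value above 5.5; the protocol gives neither. A reader might infer a frequency from the Japanese cohort in section 1.1.1, which is described as divided into quartiles with a top group at 4.0 or higher. The Figure 3 legend shows fixed cut-points without group sizes, and the cohort's bath is not given, so no proportion follows for this trial. Section 1.2 does say that potassium can fall to 2.0 or lower during dialysis, so end values below 4.0 are foreseeable.

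The consequence is an experimental regimen whose delivered dose may depend on how a site reads one sentence. That affects dosing consistency and patient safety, and it blurs what the experimental period represents. It should be corrected.

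**What to change.** Reconcile 7.2.1, 6.9, 3.9, 3.9.1, 5.3.1 and Table 3 into one titration table that all of these sections cite. The table should state:

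- which sample drives dose changes, in both directions;
- how the below-4.0 and below-3.5 rules relate, including how many readings each needs and what *adjusted* adds;
- what *decreased* means at the lowest dispensed level, with Table 3 listing every level that results;
- what follows after two hypokalemic events, so that 6.9, 3.9 and 3.9.1 agree.

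All values and clinical rules are the sponsor's decision; this review takes no view on them. The cost is a protocol amendment and, if a level is added, a matching dispensing row. No extra samples or visits are needed, because both potassium values are already collected weekly.

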### 7.2.2 Study Drug Dispensation and Instructions for Reconstitution and Dosing

The allow for adequate dosing (including dose-titration, as described in [Section 7.2.1](#)), the study drug will be dispensed to patients on a weekly basis, as follows:

**Table 3 IP Dispensing Schedule and Dosing Instructions**

IP Dose Level	IP Packets dispensed	Instructions for Patients (For dosing on off-dialysis days):
5.0 grams, 4 days/week	4 x 5.0 g packets	On each dosing day (4 off-dialysis days per week): Dissolve in water and drink the content of one 5.0 gram packet [1]
10.0 grams, 4 days/week	8 x 5.0 g packets	On each dosing day (4 off-dialysis days per week): Dissolve in water and drink the content of two 5.0 gram packet [1]
15.0 grams, 4 days/week	12 x 5.0 g packets	On each dosing day (4 off-dialysis days per week): Dissolve in water and drink the content of three 5.0 gram packet [1]

[1] Patients should be instructed to (i) empty the entire contents of the packet(s) into a drinking glass containing approximately 3 tablespoons of water or more if desired; (ii) stir well and drink immediately; (iii) if powder remains in the drinking glass, add water, stir, and drink immediately; (iv) repeat until no powder remains to ensure the entire dose is taken.

### **7.3 Labelling**

Labels will be prepared in accordance with Good Manufacturing Practice (GMP) and local regulatory guidelines. The labels will fulfil GMP Annex 13 requirements for labelling.

### **7.4 Storage**

All study drugs should be kept in a secure place under appropriate storage conditions, at a temperature between 15°C-30°C (59°F-86°F). The study drug label will specify the appropriate storage conditions.

At the study site, study drug will be stored at the participating dialysis unit, separate from other similar agents (Patiromer).

### **7.5 Compliance**

During the 8-week “high dialysate” treatment period, patients will be asked to return to the site all used (including empty) packets of study drug (Lokelma) on a weekly basis. These will be assessed by the study coordinator to confirm treatment compliance. In case of a discrepancy between the planned vs actual number of packets used, the patient will be asked whether they had missed any of the prescribed study drug doses. Information about missed doses will be recorded in the patient’s source records. An additional “internal control” of study drug compliance will be the pre-dialysis K+ level after the long dialysis weekend. Patients reporting compliance with the study drug but K+ above the 5.5 mEq/L goal will be up-titrated to the next Lokelma dose.

Study drug administration should also be recorded in the appropriate section of the eCRF.

### **7.6 Accountability**

The study drug (Lokelma) provided for this study will be used only as directed in this protocol.

The study nurse coordinator will be responsible for recording all study drugs dispensed to and returned by the patient. Any unused packets of study drug will either be returned to the Company under the directive of the Company, or destroyed locally upon approval by the Company, and according to applicable local Standard Operating Procedures (SOPs).

### **7.7 Concomitant and Other Treatments**

All concomitant medications must be recorded in the appropriate sections of the eCRF.

#### **7.7.1 Prohibited Treatment**

Use of the following medications is prohibited during the study:

Prohibited Medication/Class of drug	Washout Period*
Amiodarone or other anti-arrhythmic therapy	2 weeks prior to Screening

Patiromer or other drugs for treatment of hyperkalemia
--

1 week prior to Screening
---------------------------

\*Washout of the of the prohibited medications can occur after signing of informed consent as applicable.

### **7.7.2 Other concomitant treatment**

Other medication other than that described above, which is considered necessary for the subject's safety and well-being, may be given at the discretion of the Investigator, and recorded in the appropriate sections of the Case Report Form.

The study drug (Lokelma) can transiently increase gastric pH, and as a result, it can change the absorption of co-administered drugs that exhibit pH-dependent solubility. Therefore, patients who are taking other oral medications will be advised to take these medications at least 2 hours before or 2 hours after the study drug.

### **7.8 Post Study Access to Study Treatment**

Not applicable.

## **8. STATISTICAL ANALYSES**

### **8.1 Statistical Considerations**

Analyses will be performed by the Sponsor or its representatives.

A comprehensive Statistical Analysis Plan (SAP) may be prepared within 90 days of the date of the first participant enrolled, and any further changes during the course of the study will be included (reflecting the final Clinical Study Protocol, including any amendments) prior to clinical database lock.

The SAP will include a more technical and detailed description of the statistical analyses described in the following sections.

### **8.2 Sample Size Estimate**

The primary statistical hypothesis of the study is that the rate of atrial fibrillation events during hemodialysis using the 3.0 K+ dialysate bath supplemented with sodium zirconium cyclosilicate (Lokelma®) is not equal to the rate of events incurred during hemodialysis using the 2.0 K+ dialysate bath.

The sample size estimation is based upon the primary statistical hypothesis, and its details were separately documented.

With >90% power to reject the primary hypothesis, 40 subjects would need to be randomized into one of two treatment sequences in the 2x2 cross-over study using the simulation study with a 2-sided alpha of 0.05, assuming an event rate of 4.6 with the 2.0 K+ dialysate bath, an overdispersion parameter of 0.07 and a reduction of rate ratio of 25%. It is expected that 10% of randomized subjects will not complete both study periods. Accounting for this estimated 10%

attrition rate, **44 subjects** per treatment sequence or **88 subjects** in total will be randomized in the study.

### **8.3 Definitions of Analysis Sets and Analysis Periods**

The analysis of data will be based on different analysis sets according to the purpose of analysis, i.e., efficacy or safety.

#### **8.3.1 All-participants Analysis Set**

The all-participants analysis set will consist of all participants who were screened for the study.

#### **8.3.2 Full Analysis Set**

The Full Analysis Set (FAS) will include all randomized participants, with participants being analyzed as randomized, rather than as treated. All efficacy endpoints will be analyzed using the FAS.

#### **8.3.3 Safety Analysis Set**

The Safety Analysis Set will include all randomized participants who during the first treatment period (study Phase I): (i) received at least one dose of the study drug (Lokelma) during treatment with the 3.0 K+ dialysate bath; or (ii) completed Visit 2 during treatment with the 2.0 K+ dialysate bath. All safety endpoints will be analyzed using the SAS.

The number of participants in each analysis set, and the number excluded and associated reasons will be summarized by treatment group and overall. In addition, the following periods will be defined for the purpose of reporting:

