## 2.3 Safety Objectives

Safety Objective #1: Lokelma-Induced Hypokalemia	Safety Outcome Measure:
To evaluate whether the use of oral sodium zirconium cyclosilicate (Lokelma ® ) during periods when patients are receiving a 3.0 K + /2.5 Ca ++ dialysate bath is associated with hypokalemic events defined as K + <3.5 mEq/L.	➤ Total number of hypokalemic events defined as Piccolo POCT or laboratory-measured K + of < 3.5 mEq/L.
Safety Objective #2: Incidence of Dialysis-related Hypokalemia, Hypomagnesemia, Hypophosphatemia, or Low Calcium	Safety Outcome Measure:
To determine the levels of K + , Mg ++ , calcium and PO 4 during dialysis (measured promptly prior to the termination of dialysis) during experimental treatment [2] compared to standard treatment [3]. Note: Each electrolyte is its own "safety" objective independently.	➤ Number of events (measured promptly prior to the termination of dialysis) where a Piccolo POCT measurement of K + is < 3.5 mEq/L OR Ca ++ is < 7.0 mEq/L, OR Mg ++ is < 2.0 mg/dl, OR a PO 4 level is <3.0 mEq/L. All episodes where a specific electrolyte falls below the above listed threshold will be considered an "event" for that electrolyte. The total number of "events" will be recorded during the 8-week Treatment Phase-1 and the 8-week Treatment Phase-2 cross-over periods.
Safety Objective #3: Adverse Experiences	Safety Outcome Measure:
To evaluate the safety and tolerability of the experimental treatment [2] compared to standard treatment [3] based on the frequency of reported adverse experiences.	➤ Frequencies of AEs, SAEs, and withdrawals due to AEs, with focus on treatment-related events.

Abbreviations: AE=adverse event; CSCA=clinically significant cardiac arrhythmia; SAE=serious adverse event

[2] Experimental treatment (8 weeks): hemodialysis using 3.0K+/2.5 Ca++ dialysate bath, with sodium zirconium cyclosilicate (Lokelma®) supplementation on off-treatment days

[3] Standard treatment (8 weeks): hemodialysis using 2.0K+/2.5 Ca++ dialysate bath, without sodium zirconium cyclosilicate (Lokelma®) supplementation

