[2] During the treatment period (both 2-week accommodation periods and 8-week Treatment phases), a second Piccolo POCT is performed promptly before dialysis end and within 30 minutes prior to rinse back on Mondays or Tuesdays after each long dialysis weekend (i.e., weekly), to measure K+, Ca++ and PO4.

[3] Applies only to the first twenty-five (25) patients randomized receiving standard treatment (hemodialysis using 2.0K+/2.5 Ca++ dialysate bath, without Lokelma supplementation) during Treatment Phase-1. Performed weekly, on Mondays or Tuesdays after each long dialysis weekend, promptly before dialysis end and within 30 minutes prior to rinse back.

[4] Performed weekly, on Mondays or Tuesdays after each long dialysis weekend, promptly before dialysis end and within 30 minutes prior to rinse back. Mg++ levels will be determined by the local laboratory at each site.

[5] Performed (if possible) upon symptomatic muscle cramping, promptly before dialysis end and within 30 minutes prior to rinse back. Mg++ levels will be determined by the local laboratory at each site.

[6] Baseline/Randomization is conducted on Week 1 of the new Dialysate Accommodation Period 1. Crossover occurs on the same day as Week 11 of the new Dialysate Accommodate Period 2. Neither Baseline/Randomization nor Crossover will be considered a separate visit.

[7] If ILR insertion is performed more than 30 days after the last K+ Piccolo POCT determination, please contact the sponsor who will determine if an additional K+ Piccolo POCT determination will be required prior to the baseline visit. These will be handled on a case-by-case basis.

[8] Adverse events will be collected from the time of first dose of Lokelmaâ, throughout the treatment and post-treatment follow-up period, up to the last study visit.

[9] SAEs will be reported from the time the patient signed the Informed Consent Form.

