### **6.4 Recording of adverse events**

#### **6.4.1 Time period for collection of adverse events**

Adverse events will be collected from the time of first dose of Lokelma®, throughout the treatment and post-treatment follow-up period, up to the last study visit.

SAEs will be reported from the time the patient signed the Informed Consent Form.

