#### **8.5.6 Safety Analyses**

Lokelma-induced hypokalemia will be evaluated based on the total number of hypokalemic events defined as PiccoloPOCT or laboratory-measured K+ of < 3.5 mEq/L.

The incidence of dialysis-related hypokalemia, hypomagnesemia, hypophosphatemia, and low calcium will be evaluated based on the number of events promptly prior to the termination of dialysis where a PiccoloPOCT measurement of K+ is < 2.0 mEq/L OR Ca++ is < 7.0 mEq/L, OR Mg++ is < 2.0 mg/dl, OR a PO4 level is < 3.0 mEq/L. All episodes where a specific electrolyte falls below the above listed threshold will be considered an “event” for that electrolyte. The total number of “events” will be recorded during the 8-week Treatment Phase-1 and the 8-week Treatment Phase-2 cross-over periods and compared between the treatments.

Safety will also be assessed in terms of the frequency of AEs, SAEs, and withdrawals due to AEs, with focus on treatment-related events. Appropriate summaries of these data will be presented by treatment group and/or study period.

Adverse events will be coded using the Medical Dictionary for Regulatory Activities (MedDRA) system organ class (SOC) and preferred term (PT). A treatment-emergent AE

(TEAE) is defined as an AE with the start date on or after the first dose date and up to (and including) 14 days after the last dose date in each of study periods when patients received 3K Bath with Lokelma. However, when patients received 2K Bath without Lokelma, A treatment-emergent AE (TEAE) is defined as an AE with the start date on or after the first visit date and up to (and including) 14 days after the last visit date in each of study periods. Only TEAEs will be included in table summaries.

The number and percentage of participants experiencing AEs, SAEs, AEs that led to withdrawal, AEs that led to death, and the number of such events, will be summarised by SOC, PT, and treatment group and study period. The number and percentage of participants experiencing AEs will further be summarised by intensity and will be presented with the number of events at each level of intensity.

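### The Safety Analysis Set admits 3.0 K-first patients after one Lokelma dose but 2.0 K-first patients only after an undefined Visit 2, so early stops in first-period standard treatment leave every safety table

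*Protocol*

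**What the plan says.** Protocol Section 8.3.3 and the synopsis (Analysis Populations) define the Safety Analysis Set in the same terms. Membership is settled once, for "all randomized participants who during the first treatment period (study Phase I", by one of two conditions:

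- on the experimental bath, the patient "received at least one dose of the study drug (Lokelma) during treatment with the 3.0 K + dialysate bath";
- on the standard bath, the patient "completed Visit 2 during treatment with the 2.0 K + dialysate bath".

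The set has wide reach: "All safety endpoints will be analyzed using the SAS". Section 2.3 lists among the safety outcomes "Frequencies of AEs, SAEs, and withdrawals due to AEs, with focus on treatment-related events", to be compared between the two treatments.

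Three other places bear on the definition.

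- **Table 1** labels its columns by period name, study week and study day. It has no visit numbers. Footnote 6 adds "Neither Baseline/Randomization nor Crossover will be considered a separate visit".
- **Section 8.5.6** gives this definition of a treatment-emergent event for the 2.0 K bath: "AE with the start date on or after the first visit date and up to (and including) 14 days after the last visit date". The rule applies period by period. On the 3.0 K bath the window opens at the first dose.
- **Section 6.4.1** (and footnote 8 to Table 1) states "Adverse events will be collected from the time of first dose of Lokelma", while SAEs are reported from consent.

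**The concern.** The two conditions differ in kind. One Lokelma dose is an exposure criterion, met almost at once. Completing a later visit requires the patient to stay in the study. Where entry depends on staying, patients whose outcome is an early death, an SAE that ends participation or a withdrawal are the ones removed, and here the requirement falls on one bath only. Safety Objective #3 compares these same outcomes between the baths.

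The label Visit 2 occurs only in the two statements of this definition. An analyst cannot build the set from the protocol, and different readings of the label exclude different patients. This is more than detail left to the SAP, because the protocol fixes the rule and fixes it by a point that its own schedule does not contain.

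**Working it through.** The protocol gives no figure for the size of the safety set or the number excluded, so there is none to reproduce. The check sets the rules side by side and then sizes the exclusion.

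**1. Entry against event window.** Patients are named by starting bath. The Sequence A and B labels in Table 4 are the reverse of those in the synopsis and Sections 1.4 and 3.5.

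| | 3.0 K first | 2.0 K first |
|---|---|---|
| Event window opens (8.5.6) | first dose | first visit |
| Entry to safety set (8.3.3) | first dose | completion of Visit 2 |
| Interval in which an event is in the window but the patient is not yet in the set | none | first visit to Visit 2 |

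Lokelma is taken on off-dialysis days (7.2.1), so a patient on a Monday schedule starting on Day 1 can take the first dose, and enter the set, on Day 2. If Visit 2 means the second weekly visit on treatment, a 2.0 K-first patient enters at about Day 8. This takes Phase I to begin on Day 1, as Section 4.1.9 does. The synopsis (Duration of treatment) places Phase I after the two-week blanking period, which leaves a further ambiguity in when either condition can be met.

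**2. Who is lost.** A 2.0 K-first patient who stops before Visit 2 is lost. SAEs are collected from consent, so the data would exist and be left out. Read literally, a 2.0 K-first patient who misses Visit 2, continues, and takes Lokelma in Phase 2 is also lost, because entry is decided in the first period only. The protocol gives no missed-visit rate, so this second group is not sized below.

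**3. Size of the first group.** Inputs from Section 8.2: 44 patients per sequence, and 10% of randomised patients not completing both periods. Assumptions: a constant drop-out hazard over the 20 treatment weeks, and Visit 2 falling w weeks after Day 1.

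Expected number stopping before Visit 2 = 44 × (1 − 0.90^(w/20))

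| w (weeks after Day 1) | Expected number of 44 | Chance of at least one |
|---|---|---|
| 0 | 0 | 0 |
| 1 | 44 × 0.00525 = 0.23 | 21% |
| 2 | 44 × 0.01048 = 0.46 | 37% |
| 4 | 44 × 0.02085 = 0.92 | 60% |

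A straight-line spread agrees: 10% / 20 = 0.5% a week, and 44 × 0.005 = 0.22 for each week.

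**4. Under a common rule.** If 2.0 K-first patients entered at their first session on the assigned bath, none of the 44 would be excluded for stopping before Visit 2.

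**The case against.** The strongest reply is that the effect is slight and would be visible. On the most natural reading of Visit 2 the expected loss is about a quarter of one patient. The 10% is non-completion for any reason, so lost safety events are fewer still. Safety is mainly descriptive, and Section 8.3.3 requires the number excluded from each set to be reported with reasons. All of this stands and limits the weight of the point. It does not make the rule sound: deaths and adverse-event withdrawals are likely to be few in an 88-patient trial, so one omitted patient can change a table row.

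It can also be said that the 3.0 K rule has a gap of its own: a patient who stops after the first session but before the first dose is excluded too. That is correct, so the contrast is roughly Day 2 against Day 8, not zero against Visit 2. However, the 3.0 K event window also opens at the first dose, so in that arm the window and the set agree. In the 2.0 K arm they do not.

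A reader might infer more than the documents support, in three ways.

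- **That early deaths, SAEs and withdrawals are structurally zero on standard treatment.** They are not. 2.0 K-first patients who complete Visit 2 keep their earlier events, and 3.0 K-first patients meet no Visit 2 condition when they reach the 2.0 K bath in the second period.
- **That about two patients would be lost.** This needs Visit 2 to be the end of the first 10 weeks, 44 × (1 − 0.90^(10/20)) = 2.3, or half of all attrition to fall before Visit 2 in the first two weeks, 44 × 0.05 = 2.2. On-treatment visits are weekly, so the first reading would make Visit 2 roughly the tenth visit. The documents give no support for the second.
- **That redefining the set makes the adverse-event comparison fair.** Under Section 6.4.1, 2.0 K-first patients have no non-serious events collected during the first period, whoever is in the set. What this definition itself loses is mainly SAEs, deaths, withdrawals and laboratory events.

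**Conclusion.** The point holds within limits. Entry to the safety set depends on first-period bath, and for 2.0 K-first patients it requires completing a visit that the schedule does not identify. Some events that Section 8.5.6 would count on the standard bath therefore belong to patients whom Section 8.3.3 leaves out. The loss is confined to first-period 2.0 K patients who do not complete Visit 2. Among those who stop early, it is about 0.2 to 0.9 of 44 if Visit 2 falls one to four weeks after Day 1, and none if it is Day 1. These figures rest on the protocol's 10% attrition, a constant hazard over 20 weeks and an assumed date for Visit 2.

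The direction is predictable: early stops are removed from standard treatment only, so experimental treatment looks relatively worse. The point should be corrected because the remedy is cheap and the rule cannot be applied as written. It does not overturn the safety comparison.

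**What to change.** In Section 8.3.3 and the synopsis, delete the Visit 2 condition and use one rule for both baths: all randomised patients with at least one dialysis session on an assigned study bath, in either period. State that events are counted by the treatment received in each period. This also removes the dependence on what Phase I means and readmits a patient who missed one early visit but later took Lokelma. Because this rule admits some patients with no Lokelma dose, summaries specific to the drug can be restricted to those who took it.

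Align the treatment-emergent window in Section 8.5.6 with the same starting point for each bath. Separately, reconcile Section 6.4.1 and footnote 8 to Table 1 with Section 8.5.6, so that non-serious events on the 2.0 K bath are collected over the window in which they are to be counted. Refer to patients by bath until the sequence labels in Table 4 agree with the rest of the protocol.

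The set definition is a text edit in two places and needs no new data. The change to the collection rule does need additional recording for 2.0 K-first patients in the first period; editing the set cannot recover events that were never collected.
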